5. INVESTIGATIONAL PLAN

[figure not shown]
5.1 Overall Study Design

This is an open-label, dose-escalating, 48-week study assessing the safety, tolerability, bioactivity and duration of action of a single intravitreal injection of 0.1 mg (low dose), 0.25 mg (mid dose), or 0.5 mg (high dose) AXT107 in approximately 18 subjects (6 subjects per dose) with DME.

Upon providing written informed consent, subjects will be enrolled into the study with the dose-escalation strategy as depicted in [Figure 1](#). A total of 16 visits are planned in the study, including Screening (Day -14 to -1), Baseline (Day 0), and follow-up visits on Day 1 (Phone call), Week 1, Week 4, Week 8, Week 12, Week 16, Week 20, Week 24, Week 28, Week 32, Week 36, Week 40, Week 44 and Week 48. [Table I-1](#) in [Appendix I](#) provides a summary of the study visit and the procedures to be performed at each visit.

The study drug will be administered by the study Investigator at Baseline (Day 0), after completion of the Baseline assessments, including BCVA, IOP measurement, slit lamp biomicroscopy, and SD-OCT. IOP will be repeated and DFE will be completed after administration of the study drug at the Baseline visit. Post-baseline assessments will be completed as specified in Section 7 and as described in the Manual of Procedures (MOP).

Figure 1 Study Schematic

¹ DMC review of safety data at Week 1. Three subsequent subjects are to be enrolled to receive the next higher treatment dose only upon confirmation from the DMC of acceptable safety profile of the previous group.

5.1.1 Study Measures

The Safety measures are as follows:

- Adverse Events
- ETDRS BCVA
- IOP
- Slit lamp Biomicroscopy
- DFE
- Optos (at selected sites only)
- SD-OCT
- OCT-A (at selected sites only)
- Fundus Photography
- Fluorescein Angiography
- Diabetic Retinopathy Severity Scale (DRSS)
- Clinical Labs
- Vital signs
- Physical examination
- Pregnancy testing

The efficacy measures are as follows:

- Change in CST from Baseline (Day 0)
- BCVA (Mean change in ETDRS letters)
- BCVA (Proportion improving ≥ 5 , ≥ 10 , and ≥ 15 letters from Baseline (Day 0)

Refer to [Table I-1 in Appendix I](#) for a schedule of study visits and Procedures.

5.1.2 Measures to Minimize Bias

This is an open label first-in-human and dose-finding study. Randomization or masking is not employed in this study.

5.1.3 Treatment Assignment and Dose Escalation Criteria

Subjects will be sequentially assigned to receive either the low, mid, or high dose of study medication, in multiples of 3. Decision regarding dose escalation will be based upon the recommendation from the Data Monitoring Committee (DMC).

The first 3 eligible subjects will receive the low dose of AXT107 injection (Group 1). After Group 1 has completed a 7-day follow-up, the DMC will review their safety data. If an acceptable safety profile is determined by the DMC, 3 additional subjects will be enrolled to receive the mid dose of AXT107 injection (Group 2). Upon completion of a 7-day follow-up, review of the safety data, and determination of an acceptable safety profile by the DMC for Group 2, 3 additional subjects will be enrolled to receive the high dose of AXT107 injection (Group 3). After the 9 initial subjects have completed the 7-day follow-up, 9 additional subjects (3 each in each treatment group) may be enrolled. If the maximum tolerated dose (MTD) is not reached after the 0.5 mg group, a higher dose up to 1.0 mg may be tested.

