| Methodology: This is an open-label, dose-escalating, 48-week study assessing the safety, tolerability, bioactivity and duration of action of a single intravitreal injection of 0.1 mg (low dose), 0.25 mg (mid dose), or 0.5 mg (high dose) AXT107 in approximately 18 subjects (up to 6 subjects per dose) with DME. Upon providing informed consent, subjects will be sequentially enrolled into the study. Decision regarding dose escalation will be based on the recommendation from the Data Monitoring Committee (DMC). The first 3 eligible subjects will receive the low dose of AXT107 injection. After the 3 low dose subjects complete a 7-day follow-up, the DMC will review their safety data. If an acceptable safety profile is determined by the DMC, 3 additional subjects will be enrolled to receive the mid dose of AXT107 injection. Upon completion of a 7-day follow-up, review of the safety data, and determination of an acceptable safety profile by the DMC for the mid dose subjects, 3 additional subjects will be enrolled to receive the high dose of AXT107 injection. For the first 9 subjects, treatment naïve patients CANNOT be enrolled. After the 9 initial subjects have completed the 7-day follow-up, 9 additional subjects (3 each to receive the low dose, mid dose, and high dose of the study drug) who can be previously treated or treatment naïve may be enrolled. In total, approximately 18 subjects with DME will be enrolled and will be followed for 48 weeks. If the maximum tolerated dose (MTD) is not reached after the 0.5 mg group, a higher dose up to 1.0 mg may be tested. All subjects will attend a total of 16 visits: Screening (Day -14 to -1), Baseline (Day 0), Day 1 (Phone call), Week 1, Week 4, Week 8, Week 12, Week 16, Week 20, Week 24, Week 28, Week 32, Week 36, Week 40, Week 44 and Week 48. Stopping rules will be considered upon DMC decision if any of the following events are identified: 
Decrease in Early Treatment Diabetic Retinopathy Study (ETDRS) best corrected visual acuity (BCVA) of ≥ 15 letters (3-line decrease) unrelated to the natural progression of the disease and determined by the Investigator to be related to the study drug in ≥ 2 subjectsIntraocular inflammation (anterior or posterior) grade +2 or more in ≥ 2 subjects (using SUN Grading Working Group and Nussenblatt et al grading)Increase in intraocular pressure (IOP) to ≥ 30 mmHg for more than 24 hours post-injection in ≥ 2 subjects despite IOP lowering medication treatment | |

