5.1.4 Criteria for Termination of the Study (Stopping Rules)

The DMC will conduct ongoing reviews of collected safety data to determine the need for early termination of the study. Stopping rules will be incorporated if any of the following events are identified:

- Decrease in Early Treatment Diabetic Retinopathy Study (ETDRS) best corrected visual acuity (BCVA) of ≥ 15 letters (3-line decrease) unrelated to the natural progression of the disease and determined by the Investigator to be related to the study drug in ≥ 2 subjects
- Intraocular inflammation (anterior or posterior) grade +2 or more in ≥ 2 subjects (using SUN Grading Working Group and Nussenblatt et al grading)
- Increase in intraocular pressure (IOP) to ≥ 30 mmHg for more than 24 hours post-injection in ≥ 2 subjects despite IOP lowering medication treatment
- Any other serious ocular or systemic adverse event (AE) that, in the opinion of the Investigator, is related to the study drug in ≥ 1 subject

Upon DMC's recommendation for study termination, further enrollment of study subjects in the study will be discontinued. Subject withdrawal procedures must be followed for all active subjects to ensure the safety of the subjects at the conclusion of the study.

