5.5.4.3 Slit Lamp Biomicroscopy

Slit lamp biomicroscopy will be performed on each eye starting at Screening (Day -14 to Day -1) and at all attended visits. Assessment of the eyelids, conjunctiva, cornea, anterior chamber, iris, and lens will be documented. At the Baseline visit, the biomicroscopy examination will be performed prior to administration of AXT107.

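### In this first-in-human trial, section 5.1.3 and the synopsis state no interval or review between injections within the first three subjects at a new dose, so all three may be injected before any has a scheduled post-injection slit lamp or BCVA examination

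*Combined protocol and SAP*

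**What the plan says.** Section 3.4 identifies the trial as the first use of AXT107 in humans and says its risks are not yet well understood.

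**Dosing order.** Section 5.1.3 assigns subjects sequentially in threes, starting with: "The first 3 eligible subjects will receive the low dose of AXT107 injection (Group 1". The synopsis adds: "After the 3 low dose subjects complete a 7-day follow-up, the DMC will review their safety data". The mid and high doses follow the same pattern, and the footnote to Figure 1 ties DMC confirmation to the next higher dose. The remaining subjects at each dose come later: "After the 9 initial subjects have completed the 7-day follow-up, 9 additional subjects (3 each in each treatment group) may be enrolled". A fourth level is possible: "If the maximum tolerated dose (MTD) is not reached after the 0.5 mg group, a higher dose up to 1.0 mg may be tested". No group size or interval is stated for it.

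**Examinations.** The early visits are "Screening (Day -14 to -1), Baseline (Day 0), Day 1 (Phone call), Week 1", and Appendix I gives Week 1 a window of ±2 days. Section 5.5.4.3 states: "At the Baseline visit, the biomicroscopy examination will be performed prior to administration of AXT107". Section 5.1 also places the Day 0 BCVA before the injection. What follows the injection is stated there too: "IOP will be repeated and DFE will be completed after administration of the study drug at the Baseline visit".

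**Stopping rules.** Section 5.1.4 lists "Intraocular inflammation (anterior or posterior) grade +2 or more in ≥ 2 subjects". The vision and IOP rules also need two subjects. The rule that one subject can meet covers other serious events judged drug-related. The same section provides for ongoing DMC review of safety data.

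**The concern.** Sequential assignment fixes an order, not a spacing. The 7-day follow-up that protects the next dose group does nothing for subjects two and three of the current one, who may be injected before anything beyond the Day 0 checks is known about subject one.

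That matters because the exposure cannot be withdrawn. The drug is given once into the eye, section 3.3 reports ocular exposure in rabbits for up to 12 months, and section 5.5.4.4 allows for drug still visible at Week 48. If a reaction begins after the Day 0 visit, the first scheduled examination to look for it may come after two more subjects have received the same dose. The same gap recurs at every escalation step and at any dose up to 1.0 mg.

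**Working it through.** The plan gives no figure on this point to reproduce: section 6.4 says the sample size has no statistical basis, and no human event rate is given. The check is therefore a reading of the text, followed by an illustration of scale.

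**1. Timing.** The first scheduled post-injection slit lamp and BCVA fall at Day 7 ± 2, that is Day 5 to Day 9. The stated minimum interval between injections within a block of three is none. All three can be injected, even on one day, before any has those examinations.

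**2. What each safeguard does.**
- Day 0 post-injection IOP and fundus examination: these take place at the injection visit, so they cannot show a reaction that starts later. The anterior chamber is listed under slit lamp (5.5.4.3), not under the fundus examination (5.5.4.4).
- Day 1 call: it collects adverse events but includes no eye examination.
- 24-hour reporting (5.5.3.1): it applies to serious events.
- Ongoing DMC review (5.1.4): no timing is given, and its stated purpose is to decide on early termination.
- Numeric rules (5.1.4): one vision, inflammation or IOP event meets none of those three thresholds.

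None makes the second injection conditional on a review of the first subject.

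**3. Scale.** Let p be the assumed chance that a subject has a qualifying event by Week 1. Let d be the chance that an event in subject one is known in time and leads to subjects two and three not being injected. With X the number affected out of three:

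- P(X ≥ 2) = (1−p)p² + p(1−d)[1−(1−p)²]
- E[X] = 3p − 2dp²

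At p = 10%: d = 0 gives 0.9×0.01 + 0.1×0.19 = 0.028. With d = 0.5 it is 0.009 + 0.0095 = 0.0185. With d = 1 it is 0.009.

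| Assumed p | P(X≥2), d=0 (same day) | d=0.5 | d=1 (hold, no resumption) | E[X], d=0 | E[X], d=1 |
|---|---|---|---|---|---|
| 5% | 0.725% | 0.481% | 0.238% | 0.150 | 0.145 |
| 10% | 2.80% | 1.85% | 0.90% | 0.300 | 0.280 |
| 20% | 10.40% | 6.80% | 3.20% | 0.600 | 0.520 |
| 30% | 21.60% | 13.95% | 6.30% | 0.900 | 0.720 |

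The most that can be saved per dose group is 2p²: 0.005, 0.02, 0.08 or 0.18 subjects. The chance that at least one of the three is affected, 1−(1−p)³, is the same in every column.

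**4. Cost.** The delay per level is 5 to 9 days before review time: 15 to 27 days over three levels and 20 to 36 over four. With an assumed 1 to 5 days of review it is 6 to 14 days per level, so 18 to 42 or 24 to 56 days. With one lead subject at each of three levels and every event seen, the chance of at least one hold is 1−(1−p)³ = 14.3%, 27.1%, 48.8% or 65.7% at p = 5%, 10%, 20% or 30%.

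**The case against.** The strongest reply is that this is a design preference. The plan has small groups, DMC-gated escalation, ongoing DMC review, a rule that one related serious event can meet, Day 0 checks after injection and a Day 1 contact. Section 3.3 reports no significant ocular toxicity for up to 15 months in rabbits and 9 months in minipigs, and no systemic exposure up to 1.0 mg/eye. All of that stands, and it makes the change a precaution rather than the repair of an error.

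The benefit is also small and a best case. Same-day injection is permitted but nowhere planned. If natural spacing already catches half of first-subject events (d = 0.5), the hold saves p² per group: 0.0025 subjects at p = 5% and 0.01 at 10%, or 0.0075 and 0.03 over three levels. If the DMC lets dosing resume after a hold, the saving in that group disappears. This stands too.

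A hold tied to the protocol's own thresholds would not be triggered by a milder reaction, although the Week 1 review would bring it to light. A shorter stagger with an added early slit lamp and BCVA would also close the gap, but needs a new procedure; the Week 1 visit already exists.

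Three stronger readings are tempting and unsupported. A reader might infer that no eye examination follows injection before Week 1; IOP and a dilated fundus examination do, on Day 0. A reader might infer that a single event would go unheeded; it would be a recorded adverse event open to ongoing DMC review, and under 5.5.1 it could be classed as serious, which brings 24-hour reporting. A reader might infer that the trial certainly has no stagger; Figure 1 is not shown, and the Manual of Procedures and any DMC charter were not supplied. The visible footnote to Figure 1 describes only the gate between doses.

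**Conclusion.** The concern holds as a gap in the stated safeguards. As far as the available text shows, nothing requires the first subject at a new dose to be reviewed before the second and third are injected, and the first scheduled slit lamp and BCVA come at Day 5 to 9. It is a worthwhile, inexpensive precaution in a first-in-human trial of a dose that cannot be withdrawn.

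The gain is mainly in avoiding clusters: at assumed rates of 5% to 30%, the chance of two or more affected subjects falls from 0.7%–21.6% to 0.2%–6.3%. These are upper bounds. They assume same-day injection as the comparison, every first-subject event seen, independent events, and no resumption after a hold. The expected number affected falls little. The finding rests on the text, not on these rates. Confidence is medium because of the documents not seen.

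**What to change.** In section 5.1.3 and the synopsis, state that:

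- At each new dose level, including any dose up to 1.0 mg, one subject is injected first.
- The second and third are injected only after that subject's Week 1 examination (BCVA, slit lamp, IOP, dilated fundus examination) and adverse events to date have been reviewed by a named role.
- Further injections at that dose wait for DMC advice if that one subject has a drug-related loss of 15 or more letters, intraocular inflammation of grade +2 or more, IOP of at least 30 mmHg for over 24 hours despite treatment, or a related serious adverse event.

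No IOP check is scheduled between Day 0 and Week 1, so if Week 1 IOP is 30 mmHg or more, the decision should wait until its duration is known. If Figure 1 or the Manual of Procedures already sets an interval, move it into 5.1.3.

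The cost is amendment wording and the delays and hold probabilities worked out above; the delay is smaller if recruitment already spaces subjects. Subjects two and three may wait longer for treatment. The first nine subjects must be previously treated, and those who had anti-VEGF must already have passed the 6- or 8-week washout. Screening them on or after the first subject's injection day allows injection up to 14 days later, which leaves 14−9 = 5 to 14−5 = 9 days for review. Earlier screening, or a hold, may mean repeat screening, including fluorescein angiography and laboratory tests.

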APPENDIX I. Schedule of Visits and Procedures

Table I-1 Schedule of Visits and Procedures

| Visit Procedures | Screening | Visit 1/ Baseline | Visit 2/ Day 1 (Phone Call) | Visit 3/ Week 1 | Visit 4/ Week 4 | Visit 5/ Week 8 | Visit 6/ Week 12 | Visit 7/ Week 16 Visit 8/ Week 20 | Visit 9/ Week 24 | Visit 10/ Week 28 Visit 11/ Week 32 Visit 12/ Week 36 Visit 13/ Week 40 Visit 14/ Week 44 | Visit 15/ Week 48/ Exit |
|------------------------------------|-----------|----------------------|-----------------------------------|--------------------|--------------------|--------------------|---------------------|--|---------------------|---|-------------------------------|
| Visit Windows (Days) | -14 to -1 | 0 | 2 | ±2 | ±3 | ±7 | ±7 | ±7 | ±7 | ±7 | ±7 |
| Informed Consent ¹ | X | | | | | | | | | | |
| Inclusion/Exclusion | X | X | | | | | | | | | |
| Demographics | X | | | | | | | | | | |
| Medical/Ophthalmic History | X | | | | | | | | | | |
| Concomitant Medications | X | X | | X | X | X | X | X | X | X | X |
| Vital signs | X | X | | X | X | X | X | X | X | X | X |
| Physical Exam | X | | | | | | | | | | |
| Urine Pregnancy Test ² | X | | | | | | | | | | X |
| Clinical Labs | X | | | | | | | | X | | X |
| ADA Assay ³ | X | | | | X | | X | | | | X |
| Adverse Events ⁴ | X | X | X | X | X | X | X | X | X | X | X |
| ETDRS BCVA | OU | OU | | OU | OU | OU | OU | OU | OU | OU | OU |
| IOP | OU | OU | | OU | OU | OU | OU | OU | OU | OU | OU |
| AC Tap ⁵ | SE | | | SE | | SE | | SE | | SE ⁶ | |
| Slit lamp Biomicroscopy | OU | OU | | OU | OU | OU | OU | OU | OU | OU | OU |
| Dilated Fundus Exam ⁷ | OU | OU ⁸ | | OU | OU | OU | OU | OU | OU | OU | OU |
| AXT107 visibility ⁷ | SE | | SE | SE | SE | SE | SE | SE | SE | SE | SE |
| SD-OCT | OU | OU | | OU | OU | OU | OU | OU | OU | OU | OU |
| OCT-A ⁹ | OU | OU | | OU | OU | OU | OU | OU | OU | OU | OU |
| Fundus Photography ⁸ | OU | | | | | OU | | | OU | | OU |
| Fluorescein Angiography | OU | | | | | OU | | | OU | | OU |
| DRSS Evaluation | OU | | | | | OU | | OU | | OU | |
| Treatment assignment | | X | | | | | | | | | |
| Study drug (AXT107) administration | | SE ⁹ | | | | | | | | | |
| Home OCT ⁵ | OU | OU | | OU | OU | OU | OU | OU | OU | OU | OU |
| Home VA ⁵ | OU | OU | | OU | OU | OU | OU | OU | OU | OU | OU |

¹ The informed consent form must be signed/dated prior to performing any study procedures, including screening procedures.

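### The DMC's 7-day escalation review may have no examination later than Day 5, because Table I-1 allows the Week 1 visit at ±2 days

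*Combined protocol and SAP*

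**What the plan says.** Section 5.1.3 of the combined protocol and SAP sets the first escalation gate: "After Group 1 has completed a 7-day follow-up, the DMC will review their safety data". The synopsis says the same: "After the 3 low dose subjects complete a 7-day follow-up, the DMC will review their safety data". Both places apply the same condition to the mid-dose cohort before the high dose opens. Each step then turns on the committee's judgement: "If an acceptable safety profile is determined by the DMC". The note to Figure 1 in Section 5.1 ties this to a visit: "DMC review of safety data at Week 1".

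Expansion uses the same interval but names no DMC determination: "After the 9 initial subjects have completed the 7-day follow-up, 9 additional subjects (3 each in each treatment group) may be enrolled". Section 5.1.3 also allows a dose of up to 1.0 mg if no maximum tolerated dose has been reached, and states no separate follow-up interval for it.

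The window row of Table I-1 (Appendix I) begins "Visit Windows (Days) | -14 to -1 | 0 | 2 | ±2 | ±3". The entries follow the columns for Screening, Baseline, Day 1, Week 1 and Week 4, so Week 1 carries ±2 days. There is no exception for the first 9 subjects. Day 1 is a phone call.

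On the day of injection, Section 5.1 states that "IOP will be repeated and DFE will be completed after administration of the study drug at the Baseline visit". Section 5.5.4.3 places the slit lamp before injection: "At the Baseline visit, the biomicroscopy examination will be performed prior to administration of AXT107".

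**The concern.** The gate is stated in days of follow-up, but the examination that informs it may take place two days before the stated interval ends. After injection day, Week 1 is the first scheduled BCVA, slit lamp and SD-OCT, and the first dilated fundus examination since the one done just after injection. No section requires an examination on or after Day 7 before the DMC review.

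This is a first-in-human study with cohorts of three, and Section 3.4 acknowledges that the risks are poorly understood. A finding that the subject does not notice, such as low-grade inflammation or a modest loss of acuity, could arise on Day 6 or 7 and be absent from the data on which a higher dose is approved. The BCVA and inflammation stopping rules in Section 5.1.4 need at least two subjects, so the window alone would rarely hide a rule that had been met. Escalation depends on a broader judgement of acceptability, however, and one such finding could bear on that.

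**Working it through.** There is no power or error-rate figure to reproduce, because Section 6.4 gives the sample size no statistical basis. The check is calendar arithmetic.

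**Inputs.** Injection on Day 0 (Section 5.3.1). Follow-up of 7 days before each gate (Section 5.1.3). Week 1 window of ±2 days and Week 4 window of ±3 days (Table I-1). Three subjects per initial cohort (Section 5.1.3).

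**Stated figure.** Week 1 = Day 0 + 7 = Day 7. The nominal visit matches the 7-day gate.

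**Permitted range.** 7 − 2 = Day 5 and 7 + 2 = Day 9, so 5 allowed days. Week 4 is 28 − 3 = Day 25 to 28 + 3 = Day 31.

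| Week 1 visit on | Days of the 7 after the visit | Interval to next scheduled examination |
|---|---|---|
| Day 5 | 7 − 5 = 2 | 20 to 26 days |
| Day 6 | 7 − 6 = 1 | 19 to 25 days |
| Day 7 | 0 | 18 to 24 days |
| Day 8 | 0 | 17 to 23 days |
| Day 9 | 0 | 16 to 22 days |

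So 2 of the 5 allowed days leave part of the interval unexamined, by at most 2 of 7 days. A silent event that begins on Day 6 or 7, after a Day 5 visit, would next be looked for on schedule between 25 − 7 = 18 and 31 − 6 = 25 days after onset.

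**Subjects concerned.** Low to mid and mid to high: 2 × 3 = 6 subjects. Group 3 adds 3 subjects, whose Week 1 data bear on expansion and on any step above 0.5 mg.

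**Stopping rules concerned.** Mainly BCVA loss and inflammation, 2 of the 4 in Section 5.1.4. The IOP rule concerns pressure sustained beyond 24 hours after injection, and Day 5 is already well past that.

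**With a 0/+2 window.** Allowed days become Day 7 to Day 9 (3 instead of 5), and none leaves a gap. The latest permitted visit stays at Day 9. If a gate could otherwise have opened at a Day 5 visit, the delay is 7 − 5 = 2 days. Over the two escalations and the expansion that is at most 3 × 2 = 6 days, plus at most 2 for each cohort above 0.5 mg. If seven days must elapse anyway, the delay is nil.

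**The case against.** The strongest reply is that the gate itself is not shortened. A reader might infer from the window that escalation can proceed on Day 5. The documents do not support that: the body text requires a completed 7-day follow-up, and a general visit window in an appendix does not naturally override a specific gating condition. On the plain reading the DMC meets on or after Day 7 and has the adverse events reported by then. This stands. It secures elapsed time and reported events, but not an examination after Day 5.

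A reader might also count all three gates and 9 subjects as equally exposed. That goes too far. Expansion enrols at doses already given, and its sentence does not turn on the DMC finding the profile acceptable, so the harm of moving to a higher dose does not apply to it.

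It is also tempting to express the gap as a loss of detection probability. That would need an onset distribution, an event risk and actual visit days, none of which the documents give.

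Other safeguards are real. Subjects can volunteer symptoms (Section 5.5.2), serious events are reported within 24 hours (Section 5.5.3.1), and DMC safety review is ongoing (Section 5.1.4). Selected sites have weekly home OCT and home acuity (Sections 5.5.4.11 and 5.5.4.12), although neither replaces a slit lamp grading of inflammation. The Manual of Procedures and the DMC's working rules are not in the file and may be tighter, but that cannot be assumed.

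Finally, a later window has its own cost: it rules out a Day 5 or Day 6 look, so a silent event that began before Day 5 could be found up to 2 days later.

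**Conclusion.** The point holds in a limited form. The protocol permits an escalation decision after seven days of follow-up in which the latest scheduled ocular examination of a subject was on Day 5. The gap is at most 2 of the 7 days. It matters mainly for the two escalation gates and for any step above 0.5 mg, and secondarily for expansion.

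The consequence is small. It is confined to silent findings that arise on Days 6 to 7 and would have changed a discretionary judgement. Day 5 is permitted rather than expected, and no frequency can be estimated.

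The conclusion assumes that Week 1 means Day 7 counted from injection on Day 0, and that no document outside this file tightens the window. The restriction to the last-dosed subject matters, because subjects dosed earlier in a slowly enrolled cohort may have been examined again before the gate.

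On balance the change is worthwhile. A Day 6 to 7 event would otherwise wait 18 to 25 days for the next scheduled look, against at most 2 days' later detection of an earlier event. This is an inexpensive improvement, not a flaw that undermines the study.

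**What to change.** Add a footnote to the Week 1 column of Table I-1: for the first 9 subjects, and for any cohort dosed above 0.5 mg, the Week 1 window is 0/+2 days (Day 7 to Day 9). All other subjects keep ±2 days. The examination that the gate relies on then covers the full 7 days.

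The change adds no visit and no procedure. The price is a narrower scheduling window for those subjects, the possible short delay at each gate shown in the working, and a move of the earliest permitted first post-injection BCVA, slit lamp and SD-OCT from Day 5 to the nominal Day 7. Unscheduled visits for symptoms remain possible throughout.

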5.2 Selection and Withdrawal of Study Subjects

Approximately 18 subjects may be enrolled into the study, with 6 subjects in each of the low (Group 1), mid (Group 2), and high (Group 3) treatment dose arms. The first 9 sequential subjects MUST NOT be treatment naïve. The additional 9 subjects can be previously treated or treatment naïve.

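### The visible text requires no DMC determination of acceptable safety for the first three 0.5 mg subjects before three more receive that dose, although both earlier dose steps require one

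*Combined protocol and SAP*

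**What the plan says.** Section 5.1.3 describes three enrolment steps. Group 1 (three subjects at 0.1 mg) is followed for 7 days and the DMC reviews the safety data; then "If an acceptable safety profile is determined by the DMC, 3 additional subjects will be enrolled to receive the mid dose". The step to 0.5 mg has the same structure, resting on "determination of an acceptable safety profile by the DMC for Group 2, 3 additional subjects will be enrolled to receive the high dose". The third step adds three subjects at each of the three doses, and its condition is "After the 9 initial subjects have completed the 7-day follow-up, 9 additional subjects (3 each in each treatment group) may be enrolled". The synopsis follows the same pattern: "After the 9 initial subjects have completed the 7-day follow-up, 9 additional subjects (3 each to receive the low dose".

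Four other places bear on the point:

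- The Figure 1 footnote in 5.1 mentions a DMC review at Week 1 and continues: "Three subsequent subjects are to be enrolled to receive the next higher treatment dose only upon confirmation from the DMC". The graphic itself is not available in the text reviewed.
- Section 5.1.4 states: "The DMC will conduct ongoing reviews of collected safety data to determine the need for early termination of the study". Three of its four criteria need two subjects, for example "Intraocular inflammation (anterior or posterior) grade +2 or more in ≥ 2 subjects". The others of this kind are study-drug-related loss of 15 letters or more, and IOP of 30 mmHg or more lasting beyond 24 hours despite medication. The fourth criterion, any other related serious event, is met by one subject.
- Section 6.4 allows the number enrolled to change if dose limiting toxicities occur. It names no decision-maker and no time point.
- On who may enter the expansion, 5.2 says: "The additional 9 subjects can be previously treated or treatment naïve".

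**The concern.** At each of the first two steps enrolment waits for a positive decision: unless the DMC finds safety acceptable, nobody receives the next dose. At the expansion the stated rule is the passage of 7 days. The DMC's remaining role there is a power to halt, which leaves enrolment open unless the committee acts.

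The difference matters for the three expansion subjects at 0.5 mg. The other six receive 0.1 or 0.25 mg, and the DMC must already have accepted those doses on 7-day data before 0.5 mg could be given at all.

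Section 3.4 says the trial is first-in-human and the risks are not well understood. The treatment is a single intravitreal injection that cannot be withdrawn, and section 3.3 reports ocular exposure in rabbits for up to 12 months. Followed to the letter, the expansion rule doubles the number exposed at 0.5 mg from 3 to 6, even after one listed event at that dose, with no requirement that the DMC clear it first.

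**Working it through.** **The plan's own count.** 3 doses × 3 initial subjects + 3 doses × 3 expansion subjects = 9 + 9 = 18, or 6 per dose. This agrees with section 6.4. The sample size has no statistical basis to reproduce, and the change proposed here leaves it at 18.

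**Conditions side by side (5.1.3 and synopsis).**

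| Step | 7-day follow-up | DMC finds safety acceptable |
|---|---|---|
| 0.1 → 0.25 mg | required | required, for Group 1 |
| 0.25 → 0.5 mg | required | required, for Group 2 |
| Expansion, including 3 more at 0.5 mg | required | not stated |

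**Whether other visible text supplies the missing entry.**

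- The general sentence in 5.1.3 on following the DMC's recommendation concerns dose escalation. It would cover the optional step towards 1.0 mg, but adding subjects at 0.5 mg is not escalation.
- The footnote's confirmation requirement is limited to the next higher dose.
- Section 5.1.4 gives a review for termination, not a condition for enrolment.
- Section 6.4 assigns no decision to the DMC.
- The interim analyses in 6.6 take place only after all subjects reach Week 12, Week 24 and Week 36, too late to govern entry to the expansion.

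**What is left uncovered.** A related serious event meets a stopping criterion alone. If a listed event has already occurred at a lower dose, a second of the same type in Group 3 makes two subjects and meets its criterion, because the criteria name no dose group. What remains is exactly one non-serious case of a listed type in Group 3, with none of that type among the 6 subjects in Groups 1 and 2.

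**Illustrative size.** The documents give no event rates. Assume a per-subject probability p at 0.5 mg of 10%, 20% or 30% for one event type, a probability q at the lower doses equal to p or p/2, and independence between subjects.

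- A = P(exactly 1 of 3 in Group 3) = 3p(1−p)²
- B = P(at least 1 of the next 3 at 0.5 mg) = 1−(1−p)³
- C = P(none of 6 in Groups 1 and 2) = (1−q)⁶
- Joint probability = A × B × C

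| p | A | B | C, q = p/2 | A×B×C | C, q = p | A×B×C |
|---|---|---|---|---|---|---|
| 10% | 0.243 | 0.271 | 0.735 | 0.048 | 0.531 | 0.035 |
| 20% | 0.384 | 0.488 | 0.531 | 0.100 | 0.262 | 0.049 |
| 30% | 0.441 | 0.657 | 0.377 | 0.109 | 0.118 | 0.034 |

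The range is therefore about 5% to 11% with half the rate at lower doses, and about 3% to 5% with the same rate at all doses.

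**The case against.** The strongest reply is that the enrolment strategy is deferred to Figure 1, which is not visible. The footnote's opening mention of a Week 1 DMC review is not tied to any group, and its marker may well sit after Group 3. This stands as a limit: the point can be made only about the visible text. Even so, a review marked there would not by itself be a required determination, since the footnote asks for confirmation only before a higher dose.

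The second reply is that the DMC is reviewing throughout, can recommend termination on data below the two-subject thresholds, and that the expansion wording is permissive. This also stands. A reader might infer that the three subjects would be dosed without oversight; 5.1.4 rules that out. What differs is whether enrolment waits for a decision or continues until one is made.

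Third, some of the residual events could be judged serious under 5.5.1 as incapacity or important medical events, and would then trigger the one-subject criterion. That depends on judgement, but it narrows the gap further.

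Fourth, the arithmetic could be made to look worse. Leaving out C gives A × B = 0.066, 0.187 and 0.290. Those figures ignore the requirement of no earlier case at lower doses, without which the two-subject criterion would already be met, so they do not describe this gap. The calculation also has no time window: a DMC decision at 7 days sees only 7-day events, and if p is a longer-term rate the first term is too large.

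Last, a reader might count the first entry of treatment-naïve patients as part of the problem. Section 5.2 opens all nine expansion places to them, and six of those are at doses already accepted, so this adds little to the case for a decision specific to 0.5 mg.

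**Conclusion.** The point holds in a narrow form. On the visible text, enrolling three more subjects at 0.5 mg (3 of the 9 expansion subjects, 3 of about 18 in all) depends on elapsed follow-up alone, whereas each earlier dose step needs a DMC determination. The practical consequence is confined to one non-serious listed event at 0.5 mg with no earlier case of that type.

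The joint probabilities of about 3% to 5% and 5% to 11% rest on assumed rates and independence. They show how often the gap would be followed by a further case. They do not measure harm prevented, because the DMC might have allowed the expansion anyway, and the further case would itself bring the count to two and meet the stopping criterion.

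The conclusion rests on the contrast in wording and not on these figures. It would shrink to a matter of consistency between text and figure if Figure 1 shows a DMC decision after Group 3. The change is worth making because the stated rule is weakest at the highest planned dose and is easily corrected.

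**What to change.** In 5.1.3 and the synopsis, add a sentence such as: Further subjects at 0.5 mg will be enrolled only after the DMC has reviewed the 7-day safety data of all subjects dosed in the initial 0.5 mg group, including any who discontinued, and has determined an acceptable safety profile. Refer to the initial 0.5 mg group explicitly, because 5.2 uses Group 3 for the whole six-subject arm. Make Figure 1 and its footnote agree.

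The rule for the six further subjects at 0.1 and 0.25 mg can stay as it is. The cost is one more DMC review of the kind already planned for Groups 1 and 2, and the 0.5 mg part of the expansion waits for it. The planned number of subjects does not change.
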